9. RESEARCH DESIGN AND METHODS

We propose a **feasibility study** during the initial 2-year Planning Phase [UG3] and multicenter, randomized, triple-masked (investigators, subjects, statisticians), placebo-controlled, parallel arm, human-subjects **pragmatic clinical trial** period during the subsequent 4-year Implementation Phase [UH3] to determine if ultrasound-guided percutaneous peripheral nerve stimulation (PNS) greatly reduces or obviates postoperative opioid requirements without a concurrent increase in surgical pain. For the entire duration of the funding period we will comply with policies and practices developed by the Work Groups of the NIH-DoD-VA Pain Management Collaboratory, and we will work with the Coordinating Center in providing relevant information and material. We have included a diverse group of recruitment sites that will provide a broad, representative patient sample of active duty military members, Veterans and their families. Study participants will be recruited from 7 centers, including both U.S. military and Veterans Affairs medical centers within a wide geographic range, providing a study sample with ethnic, racial, and socioeconomic diversity.

U.S. military medical centers:

- Brooke Army Medical Center [San Antonio, Texas]
- Fort Bragg [Fayetteville, North Carolina]
- Naval Medical Center San Diego [San Diego, California]
- Walter Reed National Military Medical Center [Bethesda, Maryland]

Veterans Affairs medical centers:

- Palo Alto Veterans Affairs Medical Center [Palo Alto, California]

Civilian university medical centers:

- The Cleveland Clinic [Cleveland, Ohio]
- University California San Diego [San Diego, California]

The study protocol and materials will be approved by each center's Institutional Review Board; and, the investigation will be prospectively registered on the clinicaltrial.gov website. The study will be overseen by a Data Safety Monitoring Board comprised of two physicians familiar with the ethical conduct of clinical research and one biostatistician. The DSMB will review enrollment, study data, protocol violations, adverse events, and oversee all aspects of the clinical trial.

UG3 Planning Phase

The initial UG3 feasibility study will be a randomized, double-masked, placebo-controlled, parallel-arm, human subjects pilot study with two Specific Aims:

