The 4-year UH3 Implementation Phase will include a multicenter, randomized, triple-masked, placebo-controlled, parallel-arm, human subjects pragmatic clinical trial. The primary Specific Aim of the trial is to determine the effect of percutaneous PNS on postoperative **opioid** requirements and **analgesia** following moderate-to-severely-painful ambulatory surgery (under the usual conditions in which PNS will be applied, making this a “pragmatic trial”). Secondary Specific Aims are to determine the effect of percutaneous PNS on physical and emotional **functioning, chronic pain, and quality of life** following moderate-to-severely-painful ambulatory surgery. The definitive UH3 pragmatic clinic trial will use the same protocol as the UG3 Planning Phase feasibility study described above, with the addition of any revisions determined necessary following that initial investigation. We will work closely with the NIH-DoD-VA Pain Management Collaboratory Coordinating Center at all phases of the definitive pragmatic clinical trial, from preparation through data analysis and manuscript preparation.

The primary end points will be cumulative opioid consumption and average surgical pain (measured with a Numeric Rating Scale) within the first 7 days following surgery. The primary analyses will compare the two treatment groups, one of which will receive active stimulation while the other will receive no stimulation.

Hypothesis 1 (UH3): Opioid consumption will be significantly decreased within the first 7 days following surgery with percutaneous PNS compared with usual and customary analgesia.

Opioid analgesic consumption [oxycodone 5 mg tablets] will be recorded at all time points (**Table 2**), ***with the primary end point being the cumulative opioid dose for postoperative days 0-7*** (see statistical section for further details).

Hypothesis 2 (UH3): Surgical pain will be decreased within the first 7 days following surgery with percutaneous PNS compared with usual and customary analgesia (measured with a Numeric Rating Scale).

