Current/present, worst, least, and average pain at the surgical site will be assessed using a Numeric Rating Scale (NRS) as part of the Brief Pain Inventory (short form). The Brief Pain Inventory is an approved NINDS common data elements Scale. The use of single items (e.g., average pain) in addition to the composite score is supported by the IMMPACT recommendations for assessing pain in clinical trials. The NRS will be recorded at all time points (**Table 2**), ***with the primary end point being the mean value of the “average” pain scores for postoperative days 0-7*** (see statistical section for further details). The NRS is a highly-sensitive measure of pain intensity with numbers

ranging from 0 to 10, zero equivalent to no pain and 10 equivalent to the worst imaginable pain. The NRS has been demonstrated to be a valid and reliable measure following analgesic interventions. In addition, NRS scores correlate well with other measures of pain intensity, and demonstrate high test-retest reliability. These NRS characteristics led to recent IMMPACT consensus recommendations for use of the 10-point NRS of pain intensity for pain trials.

An additional instrument, the Defense and Veterans Pain Rating Scale (DVPRS), will be utilized at various time points following surgery. The DVPRS was developed specifically for—and subsequently validated in—active duty military and Veteran patient populations. Unfortunately, this new instrument has not been validated for repeated measures, and therefore will not be used as a primary end point for the current investigation. However, future pain-related investigations involving military personnel and Veterans will undoubtedly use the DVPRS, and we want the results of the current study to be comparable. Therefore, we will use the DVPRS as a secondary end point at various time points (not all to lessen the questionnaire burden on subjects).

Primary end point: *In order to claim that percutaneous PNS is superior to usual and customary analgesia, at least one of Hypotheses 1 and 2 above must be superior while the other either superior or at least noninferior.*

Hypothesis 3 (UH3): Physical and emotional **functioning** will be significantly improved in the 12 months following ambulatory surgery with percutaneous PNS as compared with usual and customary analgesia (measured with the Brief Pain Inventory).

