Quarterly Total:	0	0	0	0	32	32	0	0	48	48	48	48	48	48	48	48	48	48	48	0	0	0	0	592	
Yearly Total:	0				64				192				192				144				0				

The Study Team (Figure 13). The study team consists of the Principal Investigator, 7 additional members of the Steering Committee, 7 Site Directors, 1 research coordinator for each of the 7 enrolling centers, and 2 Significant Contributors from the company that developed the electrical leads and stimulator.

Statistical Plan and Data Analysis

Randomized groups will be compared for balance on baseline characteristics using descriptive statistics and the standardized difference (i.e., difference in means or proportions divided by pooled standard deviation). Absolute standardized differences larger than 0.10 will be considered imbalanced and the corresponding variables considered for adjustment in all analyses. Primary analyses will be modified intent-to-treat, such that all randomized patients who receive at least some of the study intervention will be included in the analyses. All patients will be analyzed in the group to which they were randomized.

Statistical methods will largely be the same for the Planning Phase and the Implementation Phase. As explained below, one difference is that in the planning phase focus we will be on the estimated confidence interval for the treatment effects and the variability of the outcomes, as these will be used in designing the full trial. Another is that interim analyses and more thorough subgroup analyses will be done in the Implementation Phase. Details are given below.

UG3 Planning Phase. For Specific Aim 2 we will estimate the treatment effect of PNS versus usual and customary care on pain and opioid consumption using a joint hypothesis testing framework. Specifically, we will conclude PNS is superior to usual and customary analgesia, at least one of Hypotheses 1 and 2 must be superior while the other either superior or at least noninferior.

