We will first test for noninferiority of PNS to usual care on each of the two outcomes using 1-tailed noninferiority tests. The noninferiority deltas will be 1 point (worse) in pain score and 20% higher in opioid consumption. Noninferiority will be assessed at the overall 0.05 significance level with no adjustment to the significance criterion for testing two outcomes since noninferiority is required on both outcomes – i.e., an intersection union test. A noninferiority delta of 1 point in pain score is conservative since receiver operating characteristic curve analysis has demonstrated that changes from baseline of at least 1.7 along a 10-point NRS accurately identified patients who rated improvements as “much improved” or more, compared with those who perceived no change or worsening following analgesic interventions.^{153,156,177-179}

We will assess noninferiority on pain score using a one tailed t-test which incorporates the noninferiority delta of 1 point. The estimated treatment effect for pain score will be derived from a linear mixed effects model with the outcome of patient’s “average” pain score for each day, with fixed effects for intervention (PNS vs usual care) and time (days 1 through 7), and assuming an autoregressive correlation structure among and measurements on the same patient overtime. We will then test for noninferiority with a one tailed t-test in which the numerator is the estimated treatment effect from the model minus the noninferiority delta (1), and the denominator is the standard error of the estimated treatment effect. This method will yield results similar to comparing groups on the patient mean of these seven days, but is more flexible since it allows for missing data and also directly accounts for the correlation within patient. The model also allows assessing the treatment by time interaction, but this will most likely not be of interest.^{180,181}

Cumulative opioid consumption is not typically normally distributed, but usually approximates a log-normal distribution. We therefore plan to assess the treatment effect of PNS versus usual care on the log transformed cumulative consumption through POD 7 using a simple linear regression model (equivalent to a t-test). The estimated treatment effect (i.e., difference between groups) will then be used in a noninferiority test with null and alternative hypotheses as: $H_0: \mu_1 - \mu_2 \geq \log(1.2) =$

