0.263 versus HA: $\mu_1 - \mu_2 < \log(1.2) = 0.263$, where μ_1 and μ_2 are the means of log-transformed opioid consumption for PNS and usual care, respectively, and $\mu_1 - \mu_2$ is estimated by the coefficient (i.e., beta) for PNS versus usual care in the regression model. The estimated treatment effect beta will also be an estimate of the ratio of geometric means for the two groups, assuming data for each group is log-normal with similar coefficient of variation between groups.

In the planning phase, focus will be on the estimated confidence interval for the treatment effects and the variability of the outcomes.

Secondary outcomes will be assessed using appropriate statistical methods. We will use the t-test or Wilcoxon rank sum test for physical and functioning as measured by the Brief Pain Inventory (Hypothesis 3), chi-square analyses and t-test of Wilcoxon rank sum test for incidence and intensity of chronic pain, respectively (Hypothesis 4), and Wilcoxon rank sum for quality of life measure by the World Health Organization Quality of Life-BREF Instrument.

[figure not shown]
Subgroup analysis for gender and ethnicity. There is little relevant prior experience with the study intervention in the patient population of the proposed investigation, so it is not known whether either gender or ethnicity would interact with the treatment effect. Therefore, in accord with the Human Subjects recommendations, we will assess the treatment effect of PNS on each outcome of interest within gender and ethnicity subgroups. In addition, we will analyze each anatomic location to detect variations in treatment effect among the various lead insertion sites and types of surgical procedures. We will not require a significant interaction between treatment effect and these factors, but will rather conduct the subgroup analyses for each level of sufficient size (n=30). The subgroup analyses will be the same as those conducted on the entire sample, and so would be just as valid and unbiased.

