Throughout, the significance level will be 0.05 for each hypothesis. SAS statistical software (Cary, NC) will be used for all analyses, and East 6.0 (Cytel, Inc. Cambridge, MA) for interim monitoring and sample size calculations.

UH3 Implementation Phase sample size considerations. Sample size parameters for the implementation phase will be derived from estimates in the planning phase. The sample size calculations below are conservative in that we observed a coefficient of variation for opioid consumption observed in our preliminary data of 0.48, substantially better than the assumed 0.65. It is thus quite possible that the actual sample size for the implementation phase will be smaller.

Sample size for the full trial will be chosen to allow an overall 90% power at the 0.025 significance level (since 1-tailed tests) to claim the intervention more effective than the control on postoperative opioid requirements and pain as measured by NRS pain score. In our joint hypothesis testing on these two outcomes, we power the study to have overall 90% power to detect superiority on either

outcome and at least noninferiority on both. We assume a coefficient of variation of 1.0 for opioid consumption and a standard deviation of 2 for pain score.

Power for the joint hypothesis testing will be driven by superiority tests since superiority is needed for at least 1 of the 2 outcomes. For cumulative opioid consumption through POD 3 our previous data had a coefficient of variation (CV) of 46% (mean (SD) of 28 (13) mg). Conservatively assuming a coefficient of variation of 75% through 7 days,¹⁸³ with a total N=528 we would have 90% power to detect a relative reduction of 20% in mean opioid consumption at the overall 0.025 significance level (0.0125 for each of the two 1-tailed tests for superiority), adjusting for interim analyses (N=448 before adjustment for interim analyses).

This sample size will yield high power (>0.95%) to detect superiority based on the intervention group having 1 point or more better than the control group on NRS pain score within the first 7 days, assuming a standard deviation of 2 points for mean of the “average” pain score for each patient.

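### The primary opioid test takes the log of cumulative dose and has no rule for a patient who takes 0 mg; if such patients occur, the opioid result depends on a choice the plan does not state.

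*Combined protocol and SAP*

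**What the plan says.** Hypothesis 1 (section 9, UH3 Implementation Phase) makes the cumulative opioid dose over postoperative days 0 to 7 a primary endpoint: "Opioid analgesic consumption [oxycodone 5 mg tablets] will be recorded at all time points". Under Post-hospital course the tablets are for breakthrough pain, so a patient may take none.

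The Statistical Plan assumes a roughly log-normal total and tests the effect "on the log transformed cumulative consumption through POD 7 using a simple linear regression model (equivalent to a t-test". It then says: "The estimated treatment effect beta will also be an estimate of the ratio of geometric means for the two groups". The noninferiority margin is a ratio of 1.2. The UH3 methods are to follow the UG3 methods closely. The analysis set is modified intention-to-treat: "all randomized patients who receive at least some of the study intervention will be included in the analyses".

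For success, "at least one of Hypotheses 1 and 2 above must be superior while the other either superior or at least noninferior". Sample size is set on the opioid test: "with a total N=528 we would have 90% power to detect a relative reduction of 20% in mean opioid consumption".

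The only nearby rule covers missing outcomes. There is no added constant, floor, rank test, two-part model or exclusion rule for a zero total.

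**The concern.** Opioid-free patients are an intended result. The opening of section 9 asks whether stimulation "greatly reduces or obviates postoperative opioid requirements without a concurrent increase in surgical pain". The lay summary raises an opioid-free recovery, and the Background reports one patient, after a procedure that is eligible here, who needed no opioids. The primary model is undefined for exactly these patients.

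Each unstated default has a cost:

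- **Leave the log missing.** The patients fall out of the model. That selects on the outcome, contradicts the analysis set, and can erase a benefit that consists of more opioid-free patients.
- **Add a constant.** The constant fixes how far zeros lie from everyone else, and so drives both the variance and the estimate.

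The exposed case is close to the stated aim. If opioid use falls and pain is unchanged, the joint claim rests on opioid superiority alone.

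**Working it through.** **1. Reproduce the plan's sample size.** Inputs from UH3 sample size considerations: coefficient of variation (CV) 0.75, ratio 0.80, one-sided 0.0125, power 90%.

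- Log SD = sqrt(ln(1 + 0.75²)) = sqrt(0.446) = 0.668.
- n per arm = 2 × (2.241 + 1.282)² × 0.446 / (ln 0.8)² = 2 × 12.41 × 0.446 / 0.0498 ≈ 222.5, so 223 per arm and 446 in total. The t-based version gives 448, the plan's figure.
- With the planned spending functions, four looks and non-binding futility, the inflation is 1.182: 448 × 1.182 ≈ 530, against the stated 528.

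The stated N is therefore that of a log-normal total with no zeros.

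**2. Dose scale (assumption).** The plan's earlier data through POD 3 are "mean (SD) of 28 (13) mg". At a constant daily rate, the mean through day 7 is 28 × 7/3 = 65 or 28 × 8/4 = 56 mg. Mean over median is sqrt(1 + 0.75²) = 1.25, so the median is 52 or 45 mg. I use 50 mg. With no use after POD 3 it would be 28/1.25 = 22 mg.

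**3. Why unchanged pain is the exposed case.** With 264 per arm (528/2) and pain SD 2, the standard error is 2 × sqrt(2/264) = 0.174. With no pain difference, noninferiority at 1 point has z = 1/0.174 = 5.7, so it is all but certain, while pain superiority passes only by chance (1.25%). The joint claim then equals opioid superiority, to within about a point.

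**4. Hand check, 264 per arm, fixed sample.**

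- No zeros: 0.223 / (0.668 × sqrt(2/264)) = 0.223/0.0581 = 3.84; power = Φ(3.84 − 2.24) = 94%.
- 5% zeros per arm, ratio 0.80, add 1 mg: zeros sit at ln 1 = 0, users near ln 51 = 3.93 and ln 41 = 3.71. Difference = 0.95 × (3.932 − 3.714) = 0.207. Variance = 0.95 × 0.446 + 0.0475 × (3.932² + 3.714²)/2 = 0.424 + 0.695 = 1.119, SD 1.058. z = 0.207/(1.058 × 0.0870) = 2.25; power = Φ(0.01) = 50%.
- 5% against 15% zeros, equal doses among users, add 1 mg: difference = 0.10 × 3.932 = 0.393. Mean variance = (1.158 + 2.350)/2 = 1.754, SD 1.325. z = 0.393/(1.325 × 0.0870) = 3.41; power = Φ(1.17) = 88%.

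**5. Simulation of the joint claim.** 264 per arm, fixed sample, median 50 mg, noninferiority one-sided 0.05 (margins 1 point and ln 1.2 = 0.182), superiority one-sided 0.0125 for each outcome. All zero rates are assumed. Entries are % of trials succeeding; repeat runs agree within about 3 points. A dash means not tabulated.

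| Scenario | Drop zeros | +1 mg | +2.5 mg | +5 mg | Rank |
|---|---|---|---|---|---|
| Ratio 0.80, pain unchanged, no zeros, CV 0.75 | 95 | 95 | 95 | 95 | 93 |
| Same, 1% zeros per arm | 94 | 85 | 88 | 90 | 92 |
| Same, 5% zeros per arm | 93 | 51 | 62 | 71 | 85 |
| 1% zeros per arm, CV 0.48 | – | 97 | 99 | 99.5 | – |
| 5% zeros per arm, CV 0.48 | 100 | 62 | 78 | 88 | 99 |
| Ratio 0.80, pain better by 1 point, 5% zeros per arm, CV 0.75 | 100 | 99.6 | 100 | 100 | 100 |
| Opioid use unchanged, pain better by 1 point, 5% zeros per arm, CV 0.75 | 92 | 63 | 75 | 85 | 85 |
| 5% vs 15% zeros, equal user doses, pain unchanged, CV 0.75 | 2 | 89 | 85 | 79 | 39 |

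The rank figures at CV 0.75 are stratified by site and lead location. Unstratified, the 5% row gives 87 and the last row about 41. With 5% zeros per arm, ratio 0.80 and unchanged pain, the three constants disagree on the claim in 20% of single datasets (26% at CV 0.48).

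**6. What the pilot can show.** No zeros in 64 patients is still compatible with a rate up to 1 − 0.05^(1/64) = 4.6% (one-sided 95% bound).

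**The case against.** - **Zeros may be rare.** Section 10 says opioid need usually lasts two weeks, the pilot series gives a median of 8 days to cessation, and 0 mg lies 28/13 = 2.2 SD below the earlier mean. The one observed zero is a single unpublished case, and the 4.6% bound is not evidence that zeros occur. This stands: the size is conditional.
- **CV 0.75 is deliberately cautious.** At the roughly 0.48 seen in preliminary data, the losses at 1% zeros nearly vanish. This stands; at 5% zeros the dependence on the constant remains.
- **A pain benefit protects the claim.** This stands if pain improves by 1 point and dose also falls by 20%. It does not cover unchanged pain or unchanged opioid use.
- **Masking.** A reader might infer that the analyst could steer the result. The documents do not support that for UH3: statisticians are masked, and unmasking waits until analysis is complete. Masking limits steering but supplies no rule.
- **The total is itself constructed.** Table 2 asks about the previous 24 hours and has no contact on days 5 and 6. If fentanyl and other operating and recovery room opioids on day 0 count, exact zeros become rarer. This stands and belongs in the fix.
- **A revision is planned.** Table 3 and Preparation for the UH3 Clinical Trial allow the statistical section to be revised after the pilot, but do not commit to a zero rule. Pilot patients are unmasked at two weeks, so a rule chosen then could be chosen with group results in view.

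A reader might also infer that an opioid-free active patient would receive the worst observed outcome. The conservative imputation covers missing data only, and a total of 0 mg is not missing.

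**Conclusion.** The gap is real: the primary opioid method is undefined for an outcome that the trial hopes to produce, and its literal use conflicts with the analysis set. The consequence is conditional on zeros occurring. With none, the log test is unaffected and the sample size reproduces.

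With an assumed 5% of zeros per arm, dose ratio 0.80 and unchanged pain, the joint claim succeeds in about 94% (dropped), roughly 50 to 70% (constants of 1 to 5 mg) and 85 to 87% (rank) at CV 0.75, and in 100%, 62 to 88% and 99% at CV 0.48. If the only benefit is 15% rather than 5% opioid-free patients, it succeeds in 2 to 3% (dropped), 79 to 89% (constants) and about 40% (rank). These figures rest on a 50 mg median and a fixed-sample test.

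A reader might infer that the opioid analysis is invalid in general, or that the primary claim is in jeopardy. The documents do not support either reading: they give no zero rate, they point to few zeros by day 7, and a 1-point pain gain with the planned dose reduction leaves the claim nearly intact. Severity is minor to should-fix.

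**What to change.** In the Statistical Plan, before unmasked UG3 outcome data are seen:

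1. State how the days 0 to 7 total is built from the Table 2 contacts, given none on days 5 and 6, and whether day-0 operating and recovery room opioids count.
2. State that a patient whose constructed total is 0 mg stays in the analysis and is not handled as missing.
3. Name one primary method that accepts zeros, for both opioid superiority and noninferiority, and use it at every interim look. State the log base if a log scale is kept: the printed 0.263 is log base 2 of 1.2, whereas the natural log is 0.182.
4. Add one prespecified sensitivity analysis under another zero rule, and report the opioid-free proportion by arm.
5. Recheck power with the UG3 zero fraction at the planned revision.

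The choice in item 3 is open, and each option has a price:

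- **Rank-sum test on mg.** With no zeros at 224 per arm, superiority power falls from 90.0% to 88.3% (3 lead-location strata) or 87.0% (21 site-by-lead strata). It is weak if the only benefit is more zeros, and it needs a new effect measure in place of the geometric-mean ratio. Noninferiority can be tested after multiplying control doses by 1.20; power at no true difference falls from 93.0% to 91.2% at 264 per arm.
- **One fixed constant.** It is simple, but it loses power when zeros are equal in both arms. With +5 mg and no zeros, the noninferiority error at a true ratio of 1.20 is 9.7% rather than 5%.
- **Two-part analysis** (opioid-free proportion, then log dose among users). It needs a stated rule for combining the parts.

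Any rule that keeps zeros lets extra opioid-free active patients offset higher doses among users; the plan should say whether that is intended. Otherwise the cost is wording and standard software.

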In concert with the NIH-DoD-VA Pain Management Collaboratory Coordinating Center, the statistical section for the subsequent UH3 pragmatic clinical trial will be revised to reflect the **estimated treatment effect** and treatment group means. For the initial submission, we have estimated the probable maximum sample size for budgeting and planning purposes; but, the results of the initial feasibility study will most-likely decrease the definitive UH3 pragmatic trial required sample size. The statistical section and budget will be revised to reflect any changes. Any revisions to the protocol or informed consent forms will be submitted to the DSMB, individual center IRBs and funding center's oversight body. A manuscript with the results of the pilot study will be prepared and submitted with the results concurrently uploaded to ClinicalTrials.gov. Lastly, a final UG3 period report will be prepared for the funding and oversight agencies.

UG3 Planning Phase Specific Aims. The investigation described above will accomplish the two Specific Aims of the UG3 Planning Phase:

Specific Aim 1 (UG3): To determine the **feasibility** and **optimize** the protocol of the Implementation Phase (UH3) multicenter clinical trial that will compare percutaneous PNS with usual and customary opioid-based analgesia following moderate-to-severely painful ambulatory surgery.

Specific Aim 2 (UG3): To **estimate** the **treatment effect** of percutaneous PNS on pain and opioid consumption following moderate-to-severely painful ambulatory surgery compared with usual and customary opioid-based analgesia. This will allow determination of the required **sample size** of the definitive multicenter clinical trial of the Implementation Phase (UH3).

UH3 Implementation Phase

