Planning Phase sample size considerations. The sample size for the planning phase of 64 patients will be sufficient to estimate the treatment effects of interest with moderate precision, i.e., a confidence interval width of roughly 1.1 standard deviations for each outcome measure. Confidence interval width for a standard deviation estimate will be 0.70 standard deviations. The planning phase will be sufficient to use in estimating the expected treatment effect and standard deviation for each outcome for the larger trial.

UH3 Implementation Phase. Statistical methods for the UH3 Implementation Phase will follow very closely the methods described for the UG3 Planning Phase. The main difference is that UH3 Implementation Phase will have sufficient data to conduct the subgroup analyses and also considerably more power to assess the treatment effects of interest.

Another substantive difference from the planning phase is that in the full trial we will conduct interim analyses at each 25% of the planned enrollment using a group sequential method with gamma spending function and gamma parameter of -4 (quite conservative) for efficacy and 0 (moderately aggressive) for futility (**Figure 14**). The probability of crossing a boundary for either efficacy (mainly) or futility at the first through fourth looks would be 0.10, 0.42, 0.80 and 1.0, respectively, assuming the alternative hypotheses were true.

Figure 14. Stopping boundaries for 1-tailed tests for superiority for either pain score or opioid consumption. Blue region indicates superiority (reduced opioid consumption or pain score) and pink region indicates futility (lack of superiority). Z-statistic represents strength of evidence against the null hypothesis, either ratio of means or difference in means divided by standard error.

Missing outcomes data will be summarized along with the etiology of the absence. | While very little outcomes data is expected to be missing,

analyses will be intention to treat, and imputation of missing data using methods such as multiple imputation and last observation carried forward will therefore be utilized, based on the situation. In a conservative analysis imputation will involve the conservative approach of assigning the worst observed outcome to patients in intervention groups and best observed outcomes to those in control.

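### Does printing the opioid noninferiority threshold as log(1.2) = 0.263, with no log base, widen the stated 20% margin to 30%?

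*Combined protocol and SAP*

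**What the plan says.** All of this is in section 9 of the combined protocol and SAP.

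- **Margin.** In Statistical Plan and Data Analysis, under the UG3 Planning Phase: "The noninferiority deltas will be 1 point (worse) in pain score and 20% higher in opioid consumption".
- **Scale.** "We therefore plan to assess the treatment effect of PNS versus usual care on the log transformed cumulative consumption through POD 7", by simple linear regression. The base of the logarithm is not given.
- **Threshold.** The alternative hypothesis is "\mu_1 - \mu_2 < \log(1.2) = 0.263", and the null uses the same number. The two means are those of log-transformed consumption for stimulation and usual care.
- **Reading of the coefficient.** "The estimated treatment effect beta will also be an estimate of the ratio of geometric means for the two groups". No back-transformation is shown.
- **Software.** "SAS statistical software (Cary, NC) will be used for all analyses".
- **Role in the primary claim.** The rule stated with Hypothesis 2 is that "at least one of Hypotheses 1 and 2 above must be superior while the other either superior or at least noninferior".
- **Carry-over.** "Statistical methods for the UH3 Implementation Phase will follow very closely the methods described for the UG3 Planning Phase". Under Preparation for the UH3 Clinical Trial, the plan also says that after the feasibility study "the statistical section for the subsequent UH3 pragmatic clinical trial will be revised".

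**The concern.** A log without a base, applied to log-normal data, is commonly read as the natural log. On that reading the printed decimal does not match the stated margin: the natural log of 1.2 is 0.182, while 0.263 corresponds to a ratio of 1.30. A stated back-transformation of the coefficient would normally settle the base. Here the sentence that should supply it says that beta itself estimates the ratio, which cannot be right in any base.

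The possible stake is real. Opioid noninferiority is one of the conditions for declaring stimulation superior. If the condition loosened unnoticed from 20% to 30%, a claim carried by pain could succeed with opioid use at or above the plan's own limit, in a trial meant to show opioid sparing. The definitive phase inherits these methods.

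**Working it through.** **Inputs (all from section 9).** Margin ratio 1.20; printed threshold 0.263; one-sided noninferiority level 0.05; N = 528 (448 before adjustment for interim looks) for the main trial; CV of 0.75 used for sample size, with 0.65 and 1.0 also mentioned; 20% reduction, 90% power and one-sided 0.0125 per outcome for superiority.

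**1. Reproduce the printed figure.**

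| Base | log(1.2) | Ratio implied by 0.263 |
|---|---|---|
| 2 | 0.2630 | 2^0.263 = 1.200 (20%) |
| natural | 0.1823 | exp(0.263) = 1.301 (30%) |
| 10 | 0.0792 | 10^0.263 = 1.832 (83%) |

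The plan's figure reproduces in base 2 and in neither of the other usual bases. It is not a natural-log margin of 30% in disguise: ln(1.30) = 0.2624, which would print as 0.262.

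**2. Does the base matter when it is used consistently?** Log SD = sqrt(ln(1 + CV²)). For CV 0.75 this is sqrt(ln 1.5625) = 0.668. The standard error at N = 528 is 0.668 × sqrt(4/528) = 0.0581.

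- Natural log: threshold divided by standard error = 0.1823 / 0.0581 = 3.14.
- Base 2: both are divided by ln 2 = 0.6931, so 0.2630 / 0.0838 = 3.14.

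The test is the same. Power for noninferiority at no true difference is about 93% in either base.

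**3. Sample size.** Per arm, 2 × (2.241 + 1.282)² × 0.668² / 0.2231² gives 223, or 446 in total, against the plan's 448. Base 2 gives 446 as well. The sample size therefore neither reveals the base nor depends on it.

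**4. Cost of mixing bases.** Suppose consumption is natural-log transformed and compared with 0.263. These are fixed-sample normal approximations without interim looks. The pass probability is Φ((0.263 − ln R)/SE − 1.645), where R is the true ratio.

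- R = 1.20, CV 0.75: Φ((0.263 − 0.1823)/0.0581 − 1.645) = Φ(−0.26) = 0.40, where 0.05 is intended.
- R = 1.20, CV 0.65 and CV 1.0: 0.47 and 0.30.
- R = 1.25, CV 0.75: Φ((0.263 − 0.2231)/0.0581 − 1.645) = Φ(−0.96) = 0.17.
- R = 1.30, CV 0.75: Φ((0.263 − 0.2624)/0.0581 − 1.645) = 0.05.
- Largest observed ratio that passes at CV 0.75: exp(0.263 − 1.648 × 0.0581) = 1.18, against exp(0.1823 − 1.648 × 0.0581) = 1.09 when the bases match.

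**5. The sentence about beta.** With no effect, beta is 0 and the ratio of geometric means is 1. A 20% reduction gives beta = −0.223 (natural) or −0.322 (base 2), not 0.80. The sentence is literally wrong; the ratio is exp(beta) or 2^beta. The test itself compares the difference in log means with the log threshold, so this sentence does not enter the decision.

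**The case for a change.** The strongest case for a change is that a prespecified rule should have one reading. Nothing in the text says base 2, natural log is the commoner convention, and the decimal appears in both the null and the alternative. Anyone who recomputes it in natural logs gets 0.182 and may wonder which value was meant. A mix-up would also reach the primary claim. With a true 1-point pain benefit and SD 2, pain superiority has power above 99.9% at N = 528, so the joint false-claim rate would stay near 40% at a true opioid ratio of 1.20. Naming the base would take a line or two.

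The missing label stands, and so does the arithmetic of the mixed case. The step from there to a defective threshold does not. The convention is not in the documents, and naming SAS does not fix a base. The only evidence in the documents about the base is the decimal, and it points to base 2. The 40% needs a further mistake that the plan does not prescribe: an analyst would have to take a decimal that visibly fails to equal log(1.2) on the scale in use and ignore the 20% given with it. Coding log(1.2) on the same scale as the data, or back-transforming the confidence limit and comparing it with 1.20, gives the intended test. The joint figure also assumes that stimulation gives a full 1-point pain benefit while opioid use rises by 20%.

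**Conclusion.** No change to the plan follows. The 20% margin, the expression log(1.2) and the value 0.263 agree in base 2, and the test is identical in any base used consistently. What is missing is a label that a competent analyst supplies from the 20% margin. The sentence about beta is a slip of wording that no conclusion rests on.

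If one base is used for data and threshold, the excess error is zero, and sample size and power are as planned. Only under the mixed-base mistake would the margin be 30%, with a pass rate of 30% to 47% at a true ratio of 1.20 (N = 528, CV 1.0 to 0.65, one-sided 0.05, no interim looks). For the 64-patient feasibility study the matter carries little weight, because its stated focus is the confidence interval and the variability. The plan already expects to revise the UH3 statistical section after that study, and the base and the back-transformation can be written out then as ordinary editing.

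This rests on reading the stated 20% as the governing intention, which the printed decimal supports.
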